**Confidential Information**

---

The same statistical methods as specified above for BMQ will be applied for the BMQ subscales.

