The 18-item BMQ consists of 18 questions used to screen for patients' beliefs, attitudes and concerns about their medication. The BMQ consists of two sections, the BMQ-Specific and the BMQ-General. The BMQ-Specific section comprises two 5 item subscales assessing the necessity of and the concerns about the prescribed medication for personal use (Specific-Necessity and Specific-Concerns). The BMQ-General section comprises two 4 item subscales assessing beliefs that medicines are harmful and overused by doctors in general (General-Harm and General-Overuse). The 18 items are rated on a Likert scale from 1=strongly disagree to 5 = strongly agree and the 18 items are summarized into the 4 subscale scores. The total score of each BMQ subscale will be calculated.

If for any of these subscales one single item is missing, the subscale will be calculated as the mean of the remaining items. This corresponds to replacing the missing value by the “average” of the available answers. If more than one item is missing, the respective subscore will be considered as not evaluable.

A summary table will show descriptive statistics (n, mean, median, SD, minimum and maximum) of the four scores for baseline and the post-baseline time points, as well as changes from baseline, by cirrhosis status and treatment regimen. In addition, analysis of covariance (ANCOVA) will be applied to investigate the effect of the different ABBVIE REGIMENS (\pm RBV) by cirrhosis status on BMQ endpoints using the corresponding BMQ baseline values as covariates.

Table 9 Overview of Outputs for Secondary Variables

Output Title	Output Short Name	Analysis Population
PAM-13 by Treatment Regimen and Cirrhosis Status - CP - <country>	tpam_<c>_tc_cp	Core population
BMQ by Treatment Regimen and Cirrhosis Status - CP - <country>	tbmq_<c>_tc_cp	Core population
PSP Utilization Until 12 weeks after EoT in Patients Taking Part in PSP by Treatment Regimen and Cirrhosis Status - CP - <country>	tpspu_<c>_tc_cp_ps p	Core population: Patients Taking Part in PSP
PSP Utilization and Satisfaction Until 12 weeks after EoT in Patients Taking Part in PSP by Treatment Regimen and Cirrhosis Status - CP - <country>	tpspu_<c>_tc_cp_ps p	Core population: Patients Taking Part in PSP
Impact of PSP on Treatment Completion - CP - <country>	tptc_<c>_cp	Core population

The layouts of the tables mentioned above are provided in Part II of the SAP (Table Shells).

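### SAP 4.2.7.2.2 scores complete BMQ subscales as totals but a subscale with one missing item as an item mean; followed literally, the rule makes the affected scores too small by a factor of 5 or 4

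*SAP*

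**What the plan says.** The SAP's BMQ text in 4.2.7.2.2 describes four subscales. For the two Specific scales (Necessity, Concerns): "The BMQ-Specific section comprises two 5 item subscales". For the two General scales (Harm, Overuse): "The BMQ-General section comprises two 4 item subscales". On the response format: "The 18 items are rated on a Likert scale from 1=strongly disagree to 5 = strongly agree". On scoring: "The total score of each BMQ subscale will be calculated". Protocol 9.7.5 asks for a total in the same way.

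The rule for one missing item follows in the SAP: "If for any of these subscales one single item is missing, the subscale will be calculated as the mean of the remaining items". It is then explained: "This corresponds to replacing the missing value by the" average of the answers that are available. For a larger gap: "If more than one item is missing, the respective subscore will be considered as not evaluable".

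The scores go into a table of n, mean, median, SD, minimum and maximum at baseline and afterwards, with changes from baseline. They also go into an ANCOVA of regimen effects by cirrhosis status, with the baseline BMQ value as covariate.

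The protocol states no missing-item rule for the BMQ itself. Its only pointer is "The same statistical methods as specified above for BMQ will be applied for the BMQ subscales". The methods set out above that sentence are those for the PAM-13. There the protocol adds up the raw item scores, and a missing item is replaced by the mean of the available items.

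**The concern.** Within a few lines the SAP defines the same score on two scales. If a total is a sum, a patient with all items answered is scored on 5–25 or 4–20. A patient with one item skipped is scored on 1–5. No step multiplies the mean back up by the number of items. A program that follows both sentences literally puts both kinds of value in one analysis variable.

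A patient who skips an item would then look like an extreme low scorer. If the skip occurs at one visit only, the patient shows a large false change from baseline. The means, SDs, minima, changes and ANCOVAs that include such a patient would be distorted.

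**Working it through.** The documents give no BMQ range, expected value or missing-item rate, so there is no figure of theirs to reproduce.

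**1. Ranges.** Inputs from SAP 4.2.7.2.2: items scored 1–5, with k = 5 items (Specific) or k = 4 (General). The documents do not define total; I read it as a sum.
- Sum: k × 1 to k × 5, so 5–25 for k = 5 and 4–20 for k = 4.
- Mean of the remaining items: 1–5 in both cases.

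**2. Does the rule do what its explanation says?** Let m be the mean of the k − 1 answered items. Replace the missing item by m.
- Subscale mean after replacement: [(k − 1)m + m]/k = m. The rule and its explanation agree.
- Subscale sum after replacement: (k − 1)m + m = k × m. The rule gives m, too small by a factor of exactly k.

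Listing every answer pattern with one item missing confirms this:

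| | 5-item | 4-item |
|---|---|---|
| Patterns | 5⁴ = 625 | 5³ = 125 |
| Literal rule equals mean after replacement | 625 | 125 |
| Literal rule equals sum after replacement | 0 | 0 |
| Literal value below the lowest possible sum | 624 | 105 |

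Examples: answers 4, 4, 3, 4 on a 5-item scale give 3.75 by the literal rule and 5 × 3.75 = 18.75 on the total scale. Answers 3, 2, 3 on a 4-item scale give 2.67 and 4 × 2.67 = 10.67.

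**3. Possible size (illustration; all inputs assumed).** Take a 5-item total with mean μ = 18 and SD σ = 3, and correlation r = 0.6 between visits. A fraction f of forms has exactly one item missing, independently and at the same rate at both visits. Affected totals are divided by 5. Write a = (1 − f) + f/5 and b = (1 − f) + f/25.
- Mean = aμ
- Variance V = b(σ² + μ²) − (aμ)²
- Between-visit covariance C = a²rσ²
- ANCOVA slope = C/V; residual variance = V − C²/V

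At f = 5%: a = 0.96 and b = 0.952.
- Mean = 0.96 × 18 = 17.28
- V = 0.952 × 333 − 17.28² = 18.42, so SD = 4.29
- C = 0.9216 × 5.4 = 4.98; slope = 4.98/18.42 = 0.27
- Residual variance = 18.42 − 4.98²/18.42 = 17.07, so residual SD = 4.13

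| f | Mean | SD | Residual SD |
|---|---|---|---|
| 0 | 18.00 | 3.00 | 2.40 |
| 1% | 17.86 | 3.31 | 2.90 |
| 2% | 17.71 | 3.59 | 3.28 |
| 5% | 17.28 | 4.29 | 4.13 |
| 10% | 16.56 | 5.18 | 5.10 |

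At 5%, standard errors from the ANCOVA would be about 4.13/2.40 = 1.7 times as large, and the baseline slope would be 0.27 instead of 0.60. If items were missing at follow-up only, 5% would give a residual SD of √(18.42 − (0.96 × 5.4)²/9) = 3.93.

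For a 4-item total with assumed mean 12 and SD 3, the shift is smaller: at 5% the mean is 11.55 (a shift of −0.45) and the SD 3.53.

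**The case against.** The best defence is that the SAP states its intent straight after the rule. A programmer who fills in the missing item with the patient's own average and then sums the items gets a correctly scaled score. So does one who scores every subscale as a mean. Neither document calls the total a sum or prints a range, and the table shells in Part II of the SAP, which might settle the matter, are not available here. The BMQ table reports minima, and SAP section 5 requires validated programs and plausibility checks, so a minimum of 3.75 on a 5–25 scale should be noticed.

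Much of this stands. A reader might infer that patients with a skipped item will certainly be scored on the wrong scale and that every BMQ summary and ANCOVA will be distorted. The documents do not support that. The error needs three things together: complete subscales summed, the rule programmed literally, and at least one subscale with exactly one item missing. Only outputs containing such a form are affected. With no single-item skips the effect is zero.

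The defence does not remove the inconsistency. The explanation matches the operative wording only if all subscales are scored as means, and neither document says so. Sum is the natural reading of total, and it is how the protocol builds the PAM-13 score. Plausibility checks may catch the error, but they do not correct the rule. In 20 of the 125 four-item patterns the literal value is 4 or more, so it passes as an admissible low total when the correctly scaled one would be 16–20.

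**Conclusion.** The SAP is internally inconsistent on BMQ scoring, and the one-missing-item rule gives a wrong value when followed literally. The factor of 5 or 4 is exact, given that total means sum. The effect on group results is conditional and cannot be quantified from the documents. The figures for 1–10% missingness rest on an assumed mean, SD, between-visit correlation and independent skipping at both visits; they show only that a small proportion of affected forms would matter.

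The consequence is limited to the BMQ, a secondary questionnaire variable on which no sample size depends. SVR12, adherence and safety analyses are untouched. The point still deserves correction, because the SAP should yield one computable score and the present wording allows two that differ four- or fivefold.

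**What to change.** In SAP 4.2.7.2.2, state that each BMQ subscale total is the sum of its items. Replace the missing-item rule with: if exactly one item is missing, subscale score = number of items in the subscale × mean of the answered items; if more than one is missing, the subscale is not evaluable. This keeps the protocol's total score and carries out the intent that the SAP already states. Check that the table shells in Part II agree.

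Scoring all four subscales as item means for every patient would also be consistent. It departs from the total score in protocol 9.7.5, however, and would have to be declared as a change from the protocol.

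The cost is a sentence or two in the SAP and one line of code. The interim outputs listed in SAP 4.2.9 include no BMQ table, so none of them would need to be redone.

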4.2.8 Analyses of Safety

All safety variables will be summarized for patients in the SP using descriptive statistical methods stratified by treatment regimen and cirrhosis status and overall.

An overview of tables for the individual values is given in Table 12.

The layouts of the tables mentioned above are provided in Part II of the SAP (Table Shells).

4.2.8.1 *Exposure to Study Medication*

One table will show the frequencies for early discontinuation and exceedance of Abbvie Regimen or Ribavirin and the corresponding reasons for SP by treatment regimen and cirrhosis status. The Abbvie Regimen is considered to have been prematurely discontinued if actual duration is shortened for more than 7 days. The duration for taking Abbvie regimen is considered to have been exceeded if the actual duration is prolonged for more than 7 days. Furthermore, summary statistics will be generated for the duration of ABBVIE regimen taken and the duration of ribavirin taken, i.e. n, mean, median, standard deviation [SD], minimum, maximum.

Unintended medication errors, i.e. patient missed taking Paritaprevir/r-Ombitasvir or Dasabuvir for at least 7 days in a row, will be displayed by medication for the entire treatment period.

4.2.8.2 *Co-medication*

Treatments, surgical and medical procedures will be coded by AbbVie assigning appropriate preferred and class terms. Frequencies will be displayed for SP by treatment regimen and cirrhosis status.

In one table, the co-medication (preferred term) will be grouped by class. Only co-medication received during treatment specified by ABBVIE regimen will be displayed (Treatment profiles: A1, A2, C1 Drug B, C2 Drug B, C3 Drug B, D).

In another table the co-medication (preferred term) will be grouped by profile. All treatment profiles will be considered, i.e.:

- A1: Continued (A1)
- A2: Permanently discontinued during CHC treatment (A2)
- A3: Permanently discontinued prior to CHC treatment (A3)
- B: Discontinued prior to CHC treatment and reintroduced post-treatment (B)
- C1 Drug A: Permanently replaced at start of CHC treatment (C1A)
- C1 Drug B: Substitute at start of CHC treatment and discontinued during CHC treatment (C1B)
- C2 Drug A: Permanently replaced at start of CHC treatment (C2A)
- C2 Drug B: Substitute at start of CHC treatment and continued (C2B)
- C3 Drug A: Replaced during CHC treatment (C3A)
- C3 Drug B: Substitute during CHC treatment (C3B)
- D: Introduced during CHC treatment (D)
- No profile reported: No profile reported

Another table will show the associated treatment profiles for the medications of special interest. Therefore the medication will be pooled appropriately. All treatment profiles will be considered.

A further table will show the associated treated conditions, i.e.:

- Alcoholic liver disease
- Angina pectoris
- Auto-immune hepatitis
- Auto-immune skin disease
- Bipolar disorder
- Chronic kidney disease
- Cryoglobulinemia
- Depression
- Diabetes mellitus (Type 1)
- Diabetes mellitus (Type 2)
- Hemophilia
- Hepatitis B
- Hepatocellular carcinoma
- HIV
- Hypertension

- Hyperthyroidism
- Hypothyroidism
- Immunologically mediated disease
- Insulin resistance
- Kidney transplantation
- Lipid disorder
- Liver transplantation
- Metabolic syndrome
- Myocardial infarction
- Opiate substitution
- Personality disorder
- Porphyria cutanea tarda (PCT)
- Primary biliary cirrhosis
- Schistosomiasis
- Schizophrenia
- Sickle cell anemia
- Steatosis (non-alcoholic)
- Stroke
- Thalassemia
- Tuberculosis
- v. Willebrand disease
- Wilson disease
- Other

All treatment profiles will be considered.

A glossary will show the verbatim terms and the corresponding coded terms used (see Table 12).

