Univariate and multiple logistic regression (MLR) methods will be used to investigate the impact of various explanatory covariates (e.g. demographic and disease characteristics, co-morbidities, type of treating institution, and prior treatment for CHC and response outcome in treatment experienced patients) on SVR12. These analyses will be of exploratory nature, data driven, and will be performed for various CP analysis groups since not each covariate might be predictive in each patient group. Furthermore, the fact that treatment regimens will differ in the various patient groups has to be taken into account, when selecting the patient groups for each MLR analysis. Backward selection procedures will be applied to generate the final MLR models which will consider only covariates in the selection procedure with a p-value  $<0.25$  in the corresponding univariate logistic regression analysis. A p-value  $<0.05$  will be used for the covariates to stay in the model in a backward elimination step. Logistic regression methods will also be used to investigate the impact of treatment adherence on SVR12.

All safety variables will be summarized for patients in the SP using descriptive statistical methods stratified by the type of combination treatment and scheduled treatment duration.

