### **9.7.6 Tolerability Analysis**

All tolerability variables will be summarized using descriptive statistical methods for the SP stratified by type of combination treatment and scheduled treatment duration.

All SAEs, non-serious AEs and pregnancy occurrences are to be reported for patients included in the study (see Section 11.0 and 9.2.3). AEs will be coded using MedDRA.

The number and percentage of patients with treatment-emergent AEs (i.e. any reported event that begins or worsens in severity after initiation of study drug through 30 days post-study drug dosing) will be tabulated by primary MedDRA SOC and PT.

Corresponding summary tables will be provided for all serious treatment-emergent AEs.

The tabulation of the number of patients with treatment-emergent AEs by severity and relationship to study drug will also be provided. Patients reporting more than one AE for a given MedDRA PT will be counted only once for that term using the most severe incident for the severity summary table and the most related for the relationship summary table.

Patients reporting more than one type of event within a SOC will be counted only once for that SOC.

Additional details of the analysis of AEs will be specified in the SAP.

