3. STUDY DESIGN

3.1 Overview of Study Design and Dosing Regimen

This is a prospective, multi-center observational study in adult patients chronically infected with HCV receiving the interferon-free ABBVIE REGIMEN ± RBV.

University centers and outpatient clinics qualified by training and experience in the management of patients with CHC participate in this study.

The prescription of a treatment regimen is at the discretion of the physician in accordance with local clinical practice and label, is made independently from this observational study and precedes the decision to offer the patient the opportunity to participate in this study.

After written informed consent has been obtained, patient data including demographic data, HCV disease characteristics, co-morbidities, co-medication, treatment details, and laboratory assessments as recorded in the patient's medical records (source documentation) are documented in the electronic case report form (eCRF). Patients are observed for the duration of the ABBVIE REGIMEN therapy and for up to 24 weeks after treatment completion.

[figure not shown]
The observational period for patients receiving 12 weeks of ABBVIE REGIMEN is max. 36 weeks (12 weeks treatment and 24 weeks post-treatment observation) and for patients receiving 24 weeks of ABBVIE REGIMEN the observational period is max. 48 weeks (24 weeks treatment and 24 weeks post-treatment observation).

Follow-up visits, treatment, procedures and diagnostic methods follow physicians' routine clinical practice. The observational study period entails the following data collection schemes, data documented are those closest to the time windows as indicated in Figure 1:

- 12-week treatment regimen: four visits plus two interim data collection windows
- 24-week treatment regimen: four visits plus three interim data collection windows

This schedule is based on the anticipated regular follow-up for patients undergoing treatment for CHC.

Figure 1 - Study Flowchart

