- “Transition to cirrhosis” is defined by “Advanced Fibrosis”
- “Cirrhosis” is defined by “Cirrhosis”.)

CP analysis groups and related treatment regimens

The CP analysis groups are defined according to the patient's fibrosis status and genotype/subtype. The standard summaries by CP analysis groups in the CP and CPSFU population are structured follows (is not specified otherwise):

- Total (regardless of cirrhosis status)
 - (1) Total (regardless of genotype)
 - (2) G1 (Total)
 - (3) G1a (including mixed subtypes and patients with unknown subtype)
 - (4) G1b
 - (5) G4 (non-G1)
- Patients with cirrhosis
 - (6) Total (regardless of genotype)
 - (7) G1 (Total)
 - (8) G1a (including mixed subtypes and patients with unknown subtype)
 - (9) G1b
 - (10) G4 (non-G1)
- Patients without cirrhosis
 - (11) Total (regardless of genotype)
 - (12) G1 (Total)
 - (13) G1a (including mixed subtypes and patients with unknown subtype)
 - (14) G1b
 - (15) G4 (non-G1)

SP analysis groups

The SP analysis groups are defined according to the treatment regimen and patient's fibrosis status. The standard summaries by SP groups in the safety population are as follows (if not specified otherwise):

- Total (regardless of cirrhosis status)
 - (1) Total
 - (2) 2DAA w/o RBV
 - (3) 2DAA + RBV
 - (4) 3DAA w/o RBV
 - (5) 3DAA + RBV
- Patients with cirrhosis
 - (6) Total
 - (7) 2DAA w/o RBV
 - (8) 2DAA + RBV
 - (9) 3DAA w/o RBV
 - (10) 3DAA + RBV
- Patients without cirrhosis
 - (11) Total
 - (12) 2DAA w/o RBV
 - (13) 2DAA + RBV
 - (14) 3DAA w/o RBV
 - (15) 3DAA + RBV
- Patients with unknown fibrosis status
 - (16) Total
 - (17) 2DAA w/o RBV
 - (18) 2DAA + RBV
 - (19) 3DAA w/o RBV
 - (20) 3DAA + RBV

(2DAA - paritaprevir/r-ombitasvir, 3 DAA - paritaprevir/r-ombitasvir + dasabuvir, RBV – ribavirin taken, w/o RBV – no ribavirin taken)

NCP analysis groups

The summary tables for the NCP will only show the data pooled for all patients in the NCP without any subgrouping by genotype and/or fibrosis status.

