- Other co-morbidities (every patient not reporting the respective co-morbidity is considered as not having the respective co-morbidity)
 - Depression (No [reference], Yes)

- Diabetes mellitus (No [reference], Type 1/Type 2)
 - Hypertension (No [reference], Yes)
 - Immunologically mediated disease (No [reference], Yes)
 - Hypothyroidism (No [reference], Yes)
 - Alcohol use (None [reference], Yes –occasional, Yes –regular, Exdrinker)
 - Key clinical chemistry and hematology laboratory variables at baseline
 - ALT ratio (continuous, see 4.2.6.5)
 - AST ratio (continuous, see 4.2.6.5)
 - Platelets [$10^9/L$] (continuous)
 - Prior treatment status (HCV treatment naïve [reference], HCV treatment experienced)

Additionally, an interaction term for cirrhosis status and genotype will be considered. If the most recent stage of liver fibrosis status (No cirrhosis/Transition to cirrhosis vs Cirrhosis), the genotype (G4, G1b vs G1a) or the interaction of both remains in the final model, then additional MLR might be considered for the subgroups concerned, taking into account the treatment regimen (e.g. in cirrhotic G1 patients: RBV vs no RBV and 12 wks vs 24 weeks).

The categories pre-specified above could be modified in the analyses if this is supported by the data (e.g. categories could be combined, if their impact on SVR12 is similar). Furthermore, continuous variables can be replaced by categorical variables.

Adherence

Adherence will be displayed for the CP by genotype and cirrhosis status and for the SP by treatment regimen and cirrhosis status. Summary statistics (n, mean, median, standard deviation [SD], and range) will be generated for continuous variable. Numbers and percentages of patients will be presented for categorical variables.

- Adherence to Abbvie regimen (% of target dose [adherence=cumulated number of pills taken /(initial prescribed number of pills x planned duration)])
 - >105%
 - >95%--<=105%
 - >80%--<=95%
 - >50%--<=80%
 - <=50%
- Adherence to ribavirin (% of target dose [adherence=cumulated dose taken /(initial prescribed dose x planned duration)])

- >105%
 - >95%-<=105%
 - >80%-<=95%
 - >50%-<=80%
 - <=50%
- Percentage of actual treatment duration in relation to the target duration of ABBVIE regimen taken
- Deviating duration of ABBVIE regimen
 - Early discontinuation (actual duration is shortened for more than 7 days)
 - Not deviated
 - Exceedance (actual duration is prolonged for more than 7 days)

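### The SAP replaces scheduled treatment duration with cirrhosis status as a safety stratum without declaring it, so crude AE and worst-laboratory percentages pool 12- and 24-week courses

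*SAP*

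**What the plan says.** **Protocol.** Section 9.7.6 has tolerability variables "summarized using descriptive statistical methods for the SP stratified by type of combination treatment and scheduled treatment duration". The Data Analysis part of the Abstract (4.0) says the same of all safety variables, which takes in laboratory data: "stratified by the type of combination treatment and scheduled treatment duration".

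**SAP.** Section 4.2.8 states: "All safety variables will be summarized for patients in the SP using descriptive statistical methods stratified by treatment regimen and cirrhosis status and overall". Sections 4.2.8.3 (adverse events) and 4.2.8.4 (laboratory data) repeat that structure. Section 4.2.1 says: "The SP analysis groups are defined according to the treatment regimen and patient's fibrosis status". It lists 20 groups, made of 2DAA or 3DAA, with or without RBV, by fibrosis status plus totals. None is split by 12 versus 24 weeks, and no output title in Table 12 mentions duration.

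The SAP openly marks three other departures from the protocol: the upper limit of the SVR12 window (4.1.1), PCS tables in place of shift tables (4.2.8.4), and the timing of the interim analysis (4.2.9). It does not mark this one.

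**The concern.** The main safety measures are crude percentages of patients with at least one event, or with a worst value, over a window that lengthens with the course. If 12- and 24-week patients share a column, that column's percentage depends on its mix of durations as well as on risk per day. Two columns with the same daily risk but different mixes will then differ.

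These tables invite two contrasts: with versus without RBV, and cirrhotic versus non-cirrhotic. If longer courses gather on one side of either contrast, part of an exposure effect can be read as an effect of ribavirin or of liver disease. The protocol's duration stratum would have prevented this. Because other departures are declared, a reader may also assume that the safety strata follow the protocol.

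**Working it through.** The plan gives no figure for this effect, so there is none to reproduce. The only planned number used is the enrolment of 440, which is consistent with its stated basis: 417 / 0.95 = 438.9.

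**Step 1. Can both durations fall in one cell?** Yes. When it describes possible further regression models, SAP 4.2.7.2.1 gives the example "in cirrhotic G1 patients: RBV vs no RBV and 12 wks vs 24 weeks". Cirrhosis status therefore does not determine duration.

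**Step 2. Time at risk.** SAP 3.1 gives courses of 12 weeks (84 days) and 24 weeks (168 days). SAP 4.2.8.3 counts AEs to 30 days after dosing.
- AE window: 84 + 30 = 114 days against 168 + 30 = 198 days; ratio 198/114 = 1.737.
- PCS and maximum-grade window (SAP 4.2.8.4, to end of treatment): 84 against 168 days; ratio 2.

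**Step 3. Risk on the longer course at the same daily rate.** Assume a constant hazard and full treatment courses.
- AE with 30% risk on 12 weeks: 1 − 0.70^1.737 = 46.2%.
- Serious AE with 3% risk on 12 weeks: 1 − 0.97^1.737 = 5.2%.
- Worst laboratory value with 30% risk on 12 weeks: 1 − 0.70^2 = 51.0%.

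**Step 4. Pooled percentage.** With share s on 24 weeks, pooled = (1 − s) × p12 + s × p24.

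| Share on 24 weeks | AE, 30% at 12 weeks | SAE, 3% at 12 weeks | Laboratory maximum, 30% at 12 weeks |
|---|---|---|---|
| 0% | 30.0% | 3.0% | 30.0% |
| 5% | 30.8% | 3.1% | 31.1% |
| 20% | 33.2% | 3.4% | 34.2% |
| 40% | 36.5% | 3.9% | 38.4% |
| 60% | 39.7% | 4.3% | 42.6% |

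**Step 5. Which shares are plausible?** Protocol 9.7.7 expects about 95% of the interim cohort to be treated for 12 weeks. Taking the rest as 24-week patients and carrying that share to the whole study (both assumptions) gives 0.05 × 440 = 22 patients. If all 22 fell in one cell, their share would be 10% in a cell of 220, 25% in a cell of 88 and 50% in a cell of 44. The 30% AE would then show as 31.6%, 34.0% or 38.1%.

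The most plausible place for clustering is the cirrhotic 3DAA + RBV cell. Protocol 7.1 associates the 24-week course with cirrhotic genotype 1a prior null responders, in a trial where every patient took RBV. This is an inference. The documents do not give the 24-week share for any cell.

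**The case against.** **The only share in the documents gives a small effect.** At 5% on 24 weeks, a 30% AE moves by 0.8 points and a 3% SAE risk by 0.1. This stands. A reader might infer from the upper rows of the table that the reported safety percentages will be inflated by several points. The documents do not support that, because those rows need clustering in a small cell, which is assumed.

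**The constant hazard leans high.** Protocol 7.1 describes bilirubin rises that peaked by Week 1 and ALT rises that generally resolved on treatment. If every event fell within the first 114 days, the longer course would add nothing. This stands, so the figures are better read as the upper part of a range that starts at zero excess.

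**Cirrhosis status captures part of the duration difference.** If use follows Protocol 7.1, non-cirrhotic cells are nearly all 12-week, and the problem is confined to cirrhotic cells and, diluted, to the total columns. This also stands. It narrows the problem but does not remove it, given Step 1.

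**Exposure is already tabulated.** SAP 4.2.8.1 summarises actual duration by the same regimen-by-cirrhosis groups, so an attentive reader can see which cells had longer exposure. It would be too strong to say that readers are bound to misattribute the difference. But a mean or median duration does not let anyone separate 12-week from 24-week event percentages, and no exposure-adjusted rate is planned.

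**Not every safety output is affected.** Mean laboratory changes are shown by visit window, so course length hardly enters. The SAE listing and the two glossaries carry no stratum. The interim safety tables are limited to planned 12-week courses. The layouts in SAP Part II are not available here and could not be checked.

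**Conclusion.** The inconsistency is certain: the protocol names scheduled duration as a safety stratum in two places, and the SAP substitutes cirrhosis status without saying so. The consequence is conditional. Pooling can distort comparisons of TEAE, PCS and maximum-CTCAE percentages in the final analysis. The excess is about 0.8 points on a 30% AE at a 5% share of 24-week courses, and 3.2 to 9.7 points if 20% to 60% of a cell takes 24 weeks. These figures assume a constant hazard, completed courses and, for the larger ones, a share that the documents do not give.

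A reader might go further and conclude that safety comparisons across all regimen groups are unreliable. The documents do not support that: the overall column and most non-cirrhotic cells are probably little affected. The change is worth making because it restores an analysis the protocol promised, at little cost.

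**What to change.** 1. Keep the regimen-by-cirrhosis tables. State in SAP 4.2.1 and 4.2.8 that they depart from Protocol 4.0 and 9.7.6, and give the reason.
2. Add to SAP 4.2.8 tables by combination and planned duration (12 versus 24 weeks) for TEAEs, serious TEAEs, TEAEs leading to withdrawal, PCS values and maximum CTCAE grade. Four combinations by two durations make 8 columns plus totals.
3. Optionally, show exposure-adjusted rates as a supplement, with the constant-rate assumption stated. For early-onset events such rates would flatter the longer course, so they should not replace the percentages.

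Splitting all 20 SP groups by duration, up to 40 columns, is not needed. It goes beyond the protocol and, with perhaps 22 patients on 24 weeks, would leave most of the new columns empty or nearly so.

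**Cost.** SAP wording and a few extra tables, some with sparse 24-week columns. No new data are needed: SAP 4.2.9 already selects interim patients by planned duration.
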